8.3. Dose-Up and Down-Titration

The number and percentage of patients with any dosing change during the Treatment Period and for each Treatment Period visit will be presented by reason for dosing change.

Reasons for dosing changes will be presented in a data listing for the safety population.

8.4. Failure-to-Improve Criteria

Beginning with the TV3 visit and at each subsequent treatment visit (up to and including the TV13 visit) the number and percentage of patients who meet failure-to-improve criteria will be summarized.

The visit at which failure-to-improve criteria are met will be presented in a data listing for the safety population.

8.5. Rescue Medication Use

Details regarding the definition of and overall summary of rescue medications are presented in Section [7.2](#).

The number of days of use of rescue medications by study period (Pre-Treatment (after the date of last visit during the TR03 core study and prior to first dose during the TR03 extension study) and Treatment Period (Visits 2-14)) and by visit for the Treatment Period will be summarized

using descriptive statistics for both the overall number of days of use as well as for the number of days of rescue medication use for the drug classes presented in [Table 1](#).

The number of days of rescue medication use between each visit will be presented graphically for overall rescue medication use as well as for each of the drug classes presented in [Table 1](#).

The overall number of days of rescue medication use and number of days of rescue medication use for each of the drug classes presented in [Table 1](#) will be summarized using descriptive statistics. For patients with ≥ 1 day of rescue medication use, percentage of total time on study will be derived as: $[(\text{the number of days of rescue medication use})/(\text{days from the informed consent date through the fixed dose period})] * 100$. The mean for all patients on-study during the time period will be presented.

Time to first new use of rescue medication (days) will be summarized using descriptive statistics. The earliest date on or after the date of first dose of study medication on which a patient begins new rescue medication use will be considered the date of first new use of rescue medication. Time to first new rescue medication use will be derived as: $(\text{date of first new use of rescue medication} - \text{date of first dose of study medication}) + 1$. For patients who have no new rescue medication use on or after the date of their first dose of study medication time to first new use of rescue medication is not calculated.

It is recognized, however, that all of these evaluations are potentially confounded with early discontinuation that may or may not be observed among patients reporting use of rescue medications. That is, the extent and duration of use of rescue medications may, at least in part, be a function of duration of participation in the study.

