The maximum dose the patient should reach at the end of Week 2 is 120 mg BID. If this dose is tolerated (as determined by the TC2 assessment), an additional up-titration may be attempted during Week 3.

The maximum dose the patient should reach at the end of Week 3 is 180 mg BID. If this dose is tolerated, it should be maintained throughout Week 4.

The dose achieved as of the end of Treatment Week 4 will be maintained throughout the rest of the Treatment Period. This dose will be defined as the patient's "maintenance dose".

During Treatment Weeks 1-4, the decision to up-titrate the patient's dose should be made based on tolerance to study drug. If the tolerance level becomes unacceptable to either the patient or the Investigator, the dose should be reduced incrementally until tolerance is stabilized (reduce dose by 30 mg BID if at the 30 mg, 60 mg, 90 mg or 120 mg dose level and reduce by 60 mg BID if the patient is at the 180 mg dose level). Patients who do not tolerate the 180 mg BID should be down titrated to the 120 mg BID dose level and maintained there if stabilized.

Two single dose reductions or dose holds per patient is permitted during Treatment Period at the Investigator's discretion. If subsequent dose reductions or dose interruptions are needed, the Medical Monitor must be contacted. The duration of any dose hold must be discussed with the Medical Monitor.

4. Statistical Considerations

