7.3. Study Treatments

7.3.1. Study Drug Dosing

The number and percentage of patients reaching various achieved doses (30, 60, 90, 120, 150, 180 and 210 mg BID) will be summarized at each study visit beginning at the Visit 3/Week 5 study visit for the safety population. In addition, the number and percentage of patients will be presented for the highest dose achieved during the entire 50 weeks of active treatment.

Patient study drug dispensing/return and missed doses information will be presented in data listings for the safety population.

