7.3.3. Treatment Compliance

On the date of the first dose of study medication, the patient is expected to take only one dose (3 tablets) of study medication (in the evening). For the remainder of the study, patients should take two doses (6 tablets) of study medication each day (one in the morning and one in the evening).

At designated visits (i.e. Weeks 1, 3, 5, 9, 13, 17, 21, 26, 30, 34, 38, 42 and 46) patients will be distributed bottles containing study medication. Patients will return the bottles at a subsequent study visit, as instructed.

The number of tablets taken will be derived as: (total tablets dispensed across visits – total tablets returned across visits) and will be used to assess overall study compliance.

The total number of tablets planned will be derived as:
 $3 + (\text{number of days between day after first dosing day and last dosing day, inclusive}) * 6$.

Patient compliance over the entire time interval from first day of treatment until the last reported dosing date will be derived as: $(\text{number of tablets taken}/\text{number of tablets planned}) * 100\%$. Patient study compliance will be summarized using descriptive statistics overall for the safety population.

Patient compliance information will be presented in a data listing for the safety population.

8. Secondary Endpoint Analysis

Efficacy measurements will be evaluated as secondary endpoints in this study. The safety population will be used to evaluate the efficacy endpoints defined for this study. Eligibility for analysis of a particular endpoint will require only that the patient have a baseline value and at least one post-baseline value so that a change from baseline calculation can be obtained. All efficacy endpoints will be evaluated through the generation of descriptive summary statistics. For continuous variables, the mean, standard deviation, median, minimum, and maximum will be presented for a particular visit and for the change from baseline (Visit 1a or 1b). For categorical variables, the number and percentage of patients within each category of classification will be summarized by study visit. No formal statistical testing will be conducted.

Visit 1a or 1b will serve as the baseline visit for efficacy endpoints. Visit 1a will be the baseline for patients directly entering the Treatment Period as of Visit 1a and Visit 1b will be the baseline for patients entering the Treatment Period after participating in the Observation Period for any length of time.

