8.1.8. Change from Baseline in PAS

The PAS consists of 7 qualitative and quantitative measurements related to the examination of the skin. Type, number, distribution, affected body parts, and quantitative number of lesions in a representative body part are documented. The biggest lesion and the most representative lesion are monitored with documentation of height and area measurements. Prurigo lesion activity is recorded as a percentage based on their stage (0-4).

Separate activity classification is provided for prurigo lesions with excoriations/crusts compared to all prurigo lesions and for healed prurigo lesions compared to all prurigo lesions. The proportion of patients with each stage of classification will be summarized at each visit for each of the two activity classifications (note that PAS is not completed at the Washout/Safety and Follow-up visit). Shift from baseline to LOV and the End of Treatment visit for all patients, patients with at least 6 months of treatment, patients with at least 9 months of treatment and patients who complete treatment will also be presented for each of the two activity classifications. Shift from baseline to Visit 5/Week 13, Visit 8/Week 26 and Visit 11/Week 38 for all patients will also be presented for each of the two activity classifications.

Classification is provided for total number of prurigo lesions (not including scars). The proportion of patients at each classification level (0, 1-19, 20-100 and >100) will be summarized at each visit (note that PAS is not completed at the Washout/Safety and Follow-up visit). Shift from baseline to LOV and the End of Treatment visit for all patients, patients with at least 6

months of treatment, patients with at least 9 months of treatment and patients who complete treatment will also be presented. Shift from baseline to Visit 5/Week 13, Visit 8/Week 26 and Visit 11/Week 38 for all patients will also be summarized.

All PAS data obtained in the study will be presented in a data listing for the safety population

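### SAP 8.5 shows rescue-medication days as raw counts over visit intervals of 14, 28 and 35 days and over unequal study periods, so constant use appears to double at Visit 4

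*SAP*

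**What the plan says.** Rescue use is a declared secondary endpoint in SAP section 3.3.2: time to first use and number of days of use. Section 8.5 implements the second part in three ways.

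- A table: "The number of days of use of rescue medications by study period (Pre-Treatment" and Treatment Period, Visits 2-14), and by visit within the Treatment Period. Pre-Treatment is defined as the time "after the date of last visit during the TR03 core study and prior to first dose during the TR03 extension study".
- A graph: "The number of days of rescue medication use between each visit will be presented graphically", for all rescue medication and for each drug class in Table 1.
- One percentage of total time on study, derived for patients with at least one day of use. Its denominator runs from informed consent through the fixed dose period. The next sentence promises a mean for all patients on study in the time period, without defining that period.

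The section closes by conceding that "the extent and duration of use of rescue medications may, at least in part, be a function of duration of participation in the study". Neither the by-visit nor the by-period counts are divided by the days over which use could be counted.

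**The concern.** A count of days in an interval depends on both the rate of use and the length of the interval. The intervals here are unequal by design, and the largest change in length falls between the titration visits and the first maintenance interval. A graph of raw days will show a jump there even if no patient changes behaviour.

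The same applies by period. Pre-Treatment can be very short or last many weeks, while treatment can run to 50 weeks, so the two counts cannot be set side by side to judge whether rescue use changed on drug.

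The study has one treatment group and plans no tests, so for this endpoint the table and graph are the whole result. If they are shaped by the visit calendar, nothing else in section 8.5 puts that right.

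**Working it through.** The plan gives no figure of its own to reproduce, so the check derives the interval lengths and applies a constant rate of use.

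**Inputs**

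- Visit weeks, section 7.3.3: "At designated visits (i.e. Weeks 1, 3, 5, 9, 13, 17, 21, 26, 30, 34, 38, 42 and 46". These are 13 dispensing visits, taken as Visits 1 to 13.
- Check of the numbering: section 7.3.1 has dose summaries "beginning at the Visit 3/Week 5 study visit", and section 8.1.8 names "Visit 5/Week 13, Visit 8/Week 26 and Visit 11/Week 38". All four agree with the list.
- End of titration, section 3.4: "The dose achieved as of the end of Treatment Week 4 will be maintained throughout the rest of the Treatment Period". The interval ending at Visit 4 is therefore the first on the maintenance dose.
- End of Treatment visit: section 3.1 places it after the last week of study drug. Week 50 and Week 51 are both tried.
- Period limits, section 3.1: at most 12 weeks of observation and at most 50 weeks on drug. For patients entering from observation, the two together may not exceed 50 weeks.
- Assumption for illustration: rescue use on 2 days per week throughout. The ratios do not depend on this choice.

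**By visit**

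Interval in days = 7 × (week of this visit − week of previous visit). Raw count = interval × 2/7. Percentage = 100 × raw count / interval.

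| Interval ending at | Weeks | Days | Raw days of use | % of days |
|---|---|---|---|---|
| Visit 2 | 1-3 | 14 | 4 | 29 |
| Visit 3 | 3-5 | 14 | 4 | 29 |
| Visits 4 to 7 | 5-9, 9-13, 13-17, 17-21 | 28 each | 8 | 29 |
| Visit 8 | 21-26 | 35 | 10 | 29 |
| Visits 9 to 13 | 26-30 through 42-46 | 28 each | 8 | 29 |
| End of Treatment | 46-50 or 46-51 | 28 or 35 | 8 or 10 | 29 |

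Step at Visit 4: 8/4 = 28/14 = 2.0. Step at Visit 8: 10/8 = 35/28 = 1.25. The percentage is flat throughout.

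**By period**

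At a constant rate, the ratio of Treatment to Pre-Treatment days of use equals the ratio of the two durations. This ignores any gap between the last TR03 visit and entry, whose length the SAP does not give.

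- 12 weeks of observation leave at most 50 − 12 = 38 weeks of treatment. Raw days: 12 × 2 = 24 and 38 × 2 = 76. Ratio 76/24 = 3.2.
- 2 weeks of observation leave at most 50 − 2 = 48 weeks. Raw days: 2 × 2 = 4 and 48 × 2 = 96. Ratio 96/4 = 24.
- A patient with 12 weeks of observation who stops after 4 weeks on drug has 24 and 4 × 2 = 8 days. The ratio is 8/24 = 0.33, an apparent fall with the same constant use.

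**The case against.** Raw days are a literal reading of the declared endpoint. The study is descriptive, and section 8.5 already offers a percentage of time on study and a warning about duration of participation. Section 4.10 also calls for visit and week number in the displays, so an attentive reader could see the unequal spacing.

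Part of this stands. Raw days belong in the report, no test is affected, and week labels help. The rest does not meet the point:

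- The percentage pools pre-treatment and treatment time and is derived only for users. The sentence after it names no interval denominator.
- The warning is about early discontinuation and time in the study. Unequal visit spacing affects patients who complete every visit.
- Week labels tell the reader that the bars are not comparable but do not make them so.

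Some stronger readings are tempting but lack support. A reader might set 12 or 2 pre-treatment weeks against a full 50 weeks of treatment (50/12 = 4.2-fold, 50/2 = 25-fold). For weeks spent in observation, the 50-week cap on the combined periods rules this out. A reader might also suppose that the SAP plans a formal comparison of Pre-Treatment with Treatment, or that it would present the Visit 4 step as loss of effect. Section 8.5 only tabulates by period and draws no such conclusion; the risk lies in how the display is read. Finally, the last interval cannot be fixed at 28 days, because the list of visit weeks stops at Week 46.

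**Conclusion.** The point holds as a flaw of presentation in a declared secondary endpoint. At any constant rate of use, the by-visit table and graph show a 2.0-fold step at Visit 4 and a 1.25-fold step at Visit 8. By period, the counts mainly reflect duration: about 3.2-fold for 12 against 38 weeks and 24-fold for 2 against 48.

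The by-visit figures rest on visits taking place in the listed weeks and on intervals observed in full. For patients entering from observation, section 3.1 refers the assignment of treatment visits to a protocol table that is not at hand, so the interval list is confirmed only for direct entrants. Section 4.2 sets no visit windows, so actual intervals will vary around these lengths. The by-period figures assume the maximum treatment time allowed and no gap after the last TR03 visit. No inferential result is affected.

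**What to change.** In section 8.5, keep the raw number of days as the declared endpoint. Beside it, by visit interval and by study period, overall and for each Table 1 drug class, add:

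100 × days of rescue use / the patient's own observed days in that interval or period.

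The definition should state that:

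- numerator and denominator are cut at the same start and end dates, since otherwise use between last dose and the next visit could push the percentage above 100;
- a visit interval runs from the previous visit to the earlier of the next visit or last dose;
- Pre-Treatment runs from after the last TR03 visit to before the first extension dose;
- patients observed in the interval or period with no rescue use count as 0%.

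Use this percentage for the by-visit graph.

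The cost is SAP wording, a small amount of extra programming and one more row per table. The visit, dosing and rescue-use dates are those that section 8.5 already needs.

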3.3.2. Secondary Endpoints

Visit 1a or Visit 1b will serve as the baseline visit for efficacy endpoints. Visit 1a will be the Baseline for patients directly entering the Treatment Period as of Visit 1a. Visit 1b will be the Baseline for patients entering the Treatment Period after participating in the Observation Period for any length of time.

The secondary endpoints are:

- Assess skin lesion improvement using the metrics of the PAS
- Change from Baseline in PRO measures Worst itch NRS, average itch intensity NRS, VRS (itchy, burning and stinging), MOS-Sleep-R, ItchyQoL, HADS by Treatment Period study visit and Baseline NRS score
- Change between Baseline and the final Treatment Period visit in PBI-P
- A description of the percentage of patients utilizing various doses of nalbuphine HCl ER tablets by study week
- A description of the frequency and reasons for dose up-and down-titration and treatment discontinuation during the study
- Frequency and distribution by time on study of patients determined to meet failure-to-improve criterion
- Changes in the PRO measurements during the Washout Period after cessation of treatment of nalbuphine HCl ER tablets
- Time to first use of rescue medications and the number of days of use of rescue medications for itching
- To evaluate the daily changes in the SOWS during the Washout Period after cessation of treatment of nalbuphine HCl ER tablets.

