7.2. Rescue Anti-Pruritic Medications

Rescue medications will be defined as those drugs, when used for the purpose of treating itch, that were required to be washed out prior to entry into TR03 as described in the protocol. For the purposes of this study, any ultraviolet (UV) light treatment received will also be defined as a rescue medication. If a medication is prescribed for chronic anti-pruritic use of greater than 2 weeks, the patient should be discontinued as described in the protocol.

Concomitant use of medications for pruritus is not prohibited except as described in the protocol. Details pertaining to the use of opiate medications are also discussed in the protocol. The list of protocol-defined rescue medications for itching is presented in [Table 1](#).

For drugs that may be used for multiple indications including pruritus, a drug is only considered a rescue medication if taken for pruritus. Use of rescue medications will not preclude continuation in the study; however, all uses of such medication along with their indication for use will be recorded. Patients will be provided a log on which to record use of rescue medications.

Table 1: List of Rescue Medications for Itching

Table 1: Rescue Medications for Itching		
Rescue Medication	Only intended for anti-pruritic treatment	Examples
Opioid receptor antagonists		naltrexone, naloxone
Antihistamines	✓	topical or systemic
Topical calcineurin inhibitors	✓	tacrolimus
Topical antibiotics	✓	---
Topical steroids	✓	---
Topical capsaicin	✓	---
Anti-septic baths and anti-septic cleansing lotions	✓	---
Anti-convulsant class drugs	✓	gabapentin or pregabalin
Systemic Steroids	✓	---
cyclosporin A and other immunosuppressants	✓	---
antidepressant medications	✓	paroxetine, fluvoxamine, amitriptyline
Malignant tumor related active treatment with a systemic drug	✓	---
UV Therapy	✓	---

The total number of rescue medications subsequent to the first dose of treatment with study medication and the number and percentage of patients using at least one rescue medication subsequent to the first dose of treatment with study medication will be summarized overall for the safety population.

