Incidence of concomitant rescue medication use will be summarized for the safety population. For incidence of use, patients will be counted only once within a medication category. In addition, for incidence of use calculations, if a patient reports taking the same medication more than once, as determined by WHO Drug name, then the medication will be counted only once (incidence of use) for that WHO Drug/medication name and patient.

The prevalence of use of rescue medications will also be summarized for rescue medications for the safety population. In this construct, multiple, distinct instances when a particular rescue medication was required will be counted as the number of times reported.

Antihistamine use across ATC classifications (a list to be furnished prior to data base lock) will also be summarized by incidence and prevalence for the safety population.

Rescue medication use will be presented separately in a data listing for the safety population.

The number and proportion of patients with rescue medication use at each visit and within ATC classification will be presented. This will be obtained by comparing the rescue medication onset date to the patient's visit dates and slotting the rescue medication accordingly. The number of days of rescue medication use will also be evaluated using descriptive statistics. Details regarding the analysis of number of days of rescue medication use are presented in Section [8.5](#).

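### Section 8.5 computes time to first new rescue use only in patients who used rescue, without censoring, so it does not estimate the declared endpoint in the Safety population

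*SAP*

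**What the plan says.** SAP Section 3.3.2 lists as a secondary endpoint "Time to first use of rescue medications and the number of days of use of rescue medications for itching". Section 4.6.2 makes the Safety population the basis for the efficacy endpoints.

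For the first component, Section 8.5 states: "Time to first new use of rescue medication (days) will be summarized using descriptive statistics". The clock starts at first dose and stops at the first new rescue use. For patients with no new use on or after the "date of their first dose of study medication time to first new use of rescue medication is not calculated". No censoring rule, Kaplan-Meier estimate or cumulative incidence is given. Section 8.5 closes by conceding that the rescue evaluations may be confounded with early discontinuation, but provides no method for it.

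Three other rescue summaries bear on the point:

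- Section 7.2 reports the "number and percentage of patients using at least one rescue medication subsequent to the first dose of treatment with study medication".
- Section 7.2 also says: "The number and proportion of patients with rescue medication use at each visit and within ATC classification will be presented". This is "obtained by comparing the rescue medication onset date to the" visit dates.
- Section 8.5 summarises days of use by period and by visit, and adds: "The number of days of rescue medication use between each visit will be presented graphically for overall rescue medication use". It also derives a percentage of time on study whose denominator is "days from the informed consent date through the fixed dose period".

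**The concern.** A time-to-event endpoint is being summarised as if every patient had the event. Patients who never need new rescue, which is the best outcome, contribute nothing. Patients who stop early without rescue are treated the same way, although their follow-up was cut short.

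The design makes this matter:

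- Follow-up is unequal. Patients who come through the Observation Period may spend up to 12 of their 50 weeks off drug (Section 3.1).
- Stopping is linked to itch. Study drug is stopped for failure to improve in worst itch from TV3 onward (Section 3.2.1) and for anti-pruritic prescribing intended for more than 2 weeks (Section 3.2.2). The symptom that drives rescue therefore also drives follow-up time.

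Section 8.5 also narrows the declared first use to first new use, so rescue already ongoing at first dose has no stated place in the analysis.

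At stake is a declared secondary endpoint whose reported value would say little about how soon, or how often, patients in this population come to need rescue.

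**Working it through.** **Inputs.** Maximum time on drug is 50 weeks, or 350 days (Section 3.1). Dispensing visits are 2 to 5 weeks apart, mostly 4 (Section 7.3.3). The SAP states no rescue rate, discontinuation rate or sample size (Section 4.3), so it has no figure to reproduce. The rates below are assumptions, with constant and independent hazards.

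**Formulas.** Let p be the probability of rescue by day 350 without dropout, and d the probability of dropout by day 350.

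- λ = −ln(1−p)/350, μ = −ln(1−d)/350, s = λ + μ
- F = 1 − (1−p)(1−d)
- Users-only median = −ln(1−F/2)/s
- All-patient median = ln 2/λ
- Proportion observed to use rescue = (λ/s)·F

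**Step 1: dropout against risk.**

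- p = 40%, d = 30%: F = 1 − 0.6×0.7 = 0.58; s = (0.5108+0.3567)/350 = 0.002479; median = −ln(0.71)/s = 138 days.
- p = 40%, d = 60%: F = 1 − 0.6×0.4 = 0.76; s = (0.5108+0.9163)/350 = 0.004077; median = −ln(0.62)/s = 117 days.
- p = 20%, d = 30%: F = 0.44; s = 0.001657; median = −ln(0.78)/s = 150 days.
- p = 20%, d = 60%: F = 0.68; s = 0.003256; median = −ln(0.66)/s = 128 days.

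Before rounding, doubling dropout shifts the median by 20.9 days (p = 40%) and 22.3 days (p = 20%). Halving the risk shifts it by 11.8 days (d = 30%) and 10.4 days (d = 60%). The all-patient medians, 475 and 1087 days, lie beyond the study in every case.

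**Step 2: no dropout.**

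| Risk by day 350 | Users-only median (days) | All-patient median (days) |
|---|---|---|
| 20% | 165 | not reached |
| 50% | 145 | 350 |
| 70% | 125 | 202 |
| 90% | 91 | 105 |

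At 50% risk the users-only median then falls to 131, 119 and 102 days as dropout rises through 30%, 50% and 70%, while the all-patient median stays at 350.

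**Step 3: why.** The users-only median depends on p and d only through λ + μ, so it cannot tell rescue from dropout. With p = 30% and d = 70% it is 113 days; with p = 70% and d = 30% it is again 113 days. Yet the proportion observed to use rescue is 18.1% in the first case and 60.9% in the second.

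**Step 4: the by-visit count in Section 7.2.** A course of L days with a random start and visit spacing W touches on average 1 + (L−1)/W intervals; onset slotting counts one.

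- L = 14, W = 28: 1 + 13/28 = 1.46 intervals, so 68% of interval-uses are captured.
- L = 14, W = 14: 1.93 intervals, 52% captured.
- L = 84, W = 28: 3.96 intervals, 25% captured.

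**Step 5: percent of time.** The SAP names Observation, Titration, Treatment and Washout periods but does not define a fixed dose period. The denominator opens at informed consent, whereas the Pre-Treatment window used elsewhere in Section 8.5 opens after the last TR03 visit, which may be earlier. The percentage is derived for patients with at least one day of use, while the mean is to cover all patients on study.

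**The case against.** The study is single-arm and descriptive, so no comparison or test is distorted. Section 8.5 says openly that non-users have no value, and Section 7.2 reports the proportion with any rescue after first dose. Read together, these give a conditional description with its event proportion beside it, and Section 8.5 warns about early discontinuation. That is fair as far as it goes. But the proportion carries no timing and takes no account of unequal follow-up, and a warning does not supply an estimate.

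The magnitudes are illustrations. Rates, constant hazards and independent dropout are all assumed, and all-patient medians beyond 350 days would be reported only as not reached.

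A reader might infer that all by-visit rescue reporting counts only new starts, so that both components of the endpoint are misstated. The SAP does not support this. The declared second component is number of days of use, and the Section 8.5 summaries of it are not restricted to starts. Only the supportive patient count in Section 7.2 is slotted by onset. The 2-week rule also limits carry-over there for prescribed anti-pruritics, though non-prescribed use and rescue ongoing at first dose can still be missed.

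A reader might also infer that the percent-of-time measure is numerically wrong, or that the study has no fixed-dose phase. Section 3.4 has the Week 4 dose maintained thereafter, and Section 8.5 does not say that days before consent enter this numerator. What stands is an undefined term and a possible mismatch of windows.

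**Conclusion.** The main point holds: time to first new rescue use, as specified, is conditional on use and uncensored, and does not estimate time to first use in the Safety population. At assumed risks of 20% to 40% and dropout of 30% to 60%, the users-only median runs from 117 to 150 days and responds about twice as much to doubling dropout as to halving the risk. That ratio depends on the rates chosen; the inability to separate the two hazards does not, within the constant-hazard model. Dropout here is unlikely to be independent of itch, so the true distortion could differ in size.

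The onset-date rule is a secondary defect confined to one supportive table, and percent of time is a matter of definition. The change should be made, but no conclusion about safety, the primary objective, depends on it.

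**What to change.** 1. **Time to first new rescue use.** Analyse all Safety patients from first dose, following non-users to last dose date (already defined, with a fallback, in Section 7.3.2). Report cumulative incidence with 95% confidence intervals at set weeks, treating early discontinuation of study drug as a competing event and completion of planned treatment as censoring. State which event counts when rescue and stopping fall on the same date. Give Kaplan-Meier with censoring at last dose as a companion, noting that this censoring is likely informative. Any users-only summary should be labelled as such.
2. **Rescue ongoing at first dose.** Report these patients separately.
3. **By-visit count (Section 7.2).** Count a patient in every visit interval that the rescue start-to-end dates overlap, over patients still on treatment in that interval.
4. **Percent of time (Section 8.5).** Replace the undefined term, use first to last dose for both numerator and denominator, and say whether non-users enter the mean as zero.

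The cost is SAP wording and standard procedures on dates the plan already uses. This is estimation, not testing; Section 4.1 already allows 95% confidence intervals where appropriate, so the descriptive character of the study is kept.
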